8.1 Definition of Serious Adverse Events (SAE)

Serious adverse events are defined as any untoward and unexpected medical occurrence that:

- Results in death
- Is life-threatening
- Requires hospitalisation or prolongation of existing inpatients' hospitalisation
- Results in persistent or significant disability or incapacity
- Is a congenital anomaly or birth defect or
- any other important medical condition which, although not included in the above, may require medical or surgical intervention to prevent one of the outcomes listed.

NOTE: The term "life-threatening" in the definition of "serious" refers to an event in which the participant was at risk of death at the time of the event; it does not refer to an event which hypothetically might have caused death if it were more severe.

8.2 Reporting Procedures for Serious Adverse Events

If an SAE arises in the period between randomisation and the main final follow-up time-point, that is deemed related to the trial interventions, the site will complete an SAE form and record the description, date of onset, end date, severity and assessment of relatedness to trial intervention.

For the purpose of safety recording for this trial, only unexpected SAEs potentially related to the intervention will be reported immediately to the Central Trial Team. When the local research team becomes aware of an SAE in a trial participant, the Principal Investigator (PI) will review the SAE locally and make a decision about the causality (i.e. likelihood of the event to be related/attributed to the intervention). Please refer to SAE Reporting Guidelines for details on the grades of causality. Following the assessment of causality the PI will assess any related events for expectedness. If the PI assesses the SAE as unexpected and related or potentially related, the details of the event will be entered on a SAE reporting form on the database, and the research team will notify the central trial team via email or telephone within 24 hours of the PI becoming aware of the event. Once received, causality and expectedness will be confirmed by the Chief Investigator (CI) or delegate. In the event that consensus is not reached between the PI and Nominated Person about assessment of causality and expectedness, this will be escalated to the CI for further discussion. However, if no consensus decision is reached about expectedness after further discussion within 1 working day, and the SAE is judged to be unexpected by any one of either the PI, Nominated Person or CI, the event will be classified as an Unexpected Event.

Notifying ethics bodies:

UK – All SAEs (reported from sites in the UK, Australia and New Zealand) that are deemed to be unexpected and related to the trial will be notified to the Research Ethics Committee (REC) that gave a favourable opinion of the study within 15 working days by the central trial team.

Australia – All Significant Safety Issues (SSIs) that meet the definition of an urgent safety measure and occur at participating Australian sites will be reported to RCH ethics by the lead site within 72 hours of study staff becoming aware of the SSI using the Safety Report Form via the Ethics Review Manager (ERM). All SSIs that do not meet the definition of an urgent safety measure will be reported to RCH ethics within 15 days of study staff becoming aware of the SSI using the SSI using the SSI using the SAfety Report Form via ERM.

New Zealand - There is no general requirement to submit individual or expedited reports of SAEs or suspected unexpected serious adverse reactions (SUSARs) to the Health and Disability Ethics Committee (HDEC). SAEs must be included in the HDEC annual progress report as an annual safety report. SAE reporting must use clearly defined categories of protocol deviation/violations. The CI/PI must locally report through the host organisation research governance route in compliance with GCP E6, all SAEs and actions taken. Where a protocol deviation or violation meets the definition of substantial (HDEC SoP Section 11), the CI must submit it to HDEC for review. This constitutes an urgent safety measure.

All such events will also be reported to the Trial Management Group, TSC and Data & Safety Monitoring Committee at their next meetings.

8.3 Reporting Procedures for Complications

Complications (i.e. AEs and SAEs that are anticipated in the routine treatment pathway, and that we have predefined) that are foreseeable in the treatment of these fractures do not need to be reported immediately, provided they are recorded in the 'Complications' section of the Case Report Forms and/or Patient Questionnaires. For this trial, such events include the following complications (including readmission or reoperation to address them):

(a) General complications – pain, pressure areas or elbow stiffness, symptomatic instability or nonunion of the bone fragments

(b) Complications specifically related to surgery - wound infection, injury/irritation to the ulna nerve, implant irritation, screw cut-out, broken or retained metalwork and the subsequent need to remove metal pins/ screws.

9. Data Management

The data management aspects of the study are summarised here with full details described in the Data Management Plan (DMP).

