Particular note will be made of complications related to the cast (e.g. pressure areas) or surgery (e.g. pain, wound infection, injury/irritation to the ulna nerve, implant irritation, screw cut-out, broken or retained metalwork, and the subsequent need to remove metal pins/screws), including hospital admission to manage these complications. These are summarised in the Table below.

Table 10: Comparison of complications & SAEs between treatment allocations

| | Operative fixation | Non-operative treatment | | OR (95 | 5% CI) | p- value |
|--|-----------------------|----------------------------|---|--------|--------|-------------|
| | n % | n | % | Raw | Adj. | |
| Number of complications* | - | | - | - | - | - |
| Participants with complications | | | | | | |
| Wound problems (from surgery*) | | | | | | |
| Elbow stiffness | | | | | | |
| Unable to move fingers normally | | | | | | |
| Patient Reported concerns | | | | | | |
| Unable to feel fingers normally | | | | | | |
| Ulna nerve problems (little & ring | | | | | | |
| fingers) | | | | | | |
| Other | | | | | | |
| Intra-operative complications | - | | - | - | - | - |
| Participants with intra-operative | | | | | | |
| complications | | | | | | |
| Ulna nerve injury | | | | | | |
| Fragmentation of bone | | | | | | |
| Wire breakage | | | | | | |
| Anaesthesia complications | | | | | | |
| Post-operative bleeding | | | | | | |
| Screw cut-out | | | | | | |
| Other | | | | | | |
| Immobilisation complications | - | | - | - | - | - |
| Participants with immobilisation | | | | | | |
| complications | | | | | | |
| Skin complication owing to pressure | | | | | | |
| area | | | | | | |
| Discomfort | | | | | | |
| Other | | | | | | |
| Unplanned surgery/hospital | - | | - | - | - | - |
| admissions* | | | | | | |
| Participants with unplanned | | | | | | |
| surgery/hospital admissions | | | | | | |
| Fracture fixation/ revision fixation | | | | | | |
| Removal of screw(s)/wire(s) | | | | | | |
| Planned removal | | | | | | |
| Irritation | | | | | | |
| Other | | | | | | |
| Nerve exploration (isolated | | | | | | |
| procedure) Nerve exploration & screw/wire | | | | | | |
| adjustment | | | | | | |
| Nerve exploration and grafting | | | | | | |
| Debride wound/ wound infection | | | | | | |
| Microbiological confirmation of | | | | | | |
| infection | | | | | | |
| Antibiotics prescribed | | | | | | |
| Other | | | | | | |

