| | Operative fixation | | Non-operative treatment | | OR (95% CI) | | p- value |
|--------------------------------------|--------------------|---|----------------------------|---|-------------|------|-------------|
| | n | % | n | % | Raw | Adj. | |
| Number of unforeseeable SAEs* | | - | | - | - | - | - |
| Participants with unforeseeable SAEs | | | | | | | |

Radiographic outcomes and analysis will be considered in a separate document to this analysis plan.

Healthcare use: will be reported in the economic analysis and will include: missed school attendance at 6 weeks, 3 months, 6 months and 12 months and resource utilisation at 3 months, 6 months and 12 months [8]. The clinical report will only include comparative school attendance at 6 weeks, 3 months, 6 months and 12 months.

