6.7 Harms

This is a low risk, pragmatic trial where both of the interventions are in common use. Thus, we do not anticipate many SAEs. All adverse events are submitted to the SCIENCE central office ONLY if they arise 12 months post-randomisation (i.e. a period deemed related to the intervention) and they fall under the category of an SAE: events resulting in Death; Life-threatening; required hospitalisation; prolonged hospitalisation; congenital abnormality of birth defect; other important medical event which may require medical or surgical intervention to prevent one of the serious outcomes listed. SAEs potentially related and unexpected are recorded on the trial's database and assessed for seriousness, causality and expectedness (Table 11).

Table 11: List of serious adverse events

| Allocation | Diagnosis | Timing of onset of event ¹ | Description of event (including signs & symptoms) | Action taken to deal with event (including any treatment) | Reason for seriousness ² | Causality: is the event related to the intervention? ³ | Expectedness (in relation to what is known about the intervention) ⁴ |
|------------|-----------|---|---|---|--|---|---|
| | | | | | | | |
| | | | | | | | |

¹: post-randomisation weeks

²: Death; Life-threatening; required hospitalisation; prolonged hospitalisation; congenital abnormality of birth defect; other important medical event which may require medical or surgical intervention to prevent one of the serious outcomes listed.

³: Possibly related; Probably related; Definitely related

⁴: Expected; Unexpected

Only unexpected SAEs potentially related to the intervention. Adverse events that are foreseeable and are not SAEs are recorded in the Complications section and are reported as outcomes.

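### SAP Table 10 plans an odds ratio and p-value for unforeseeable SAEs, but for ulna nerve events foreseeability depends on whether the child had surgery

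*Protocol*

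**What the plan says.** Protocol 8.3 defines a class of predefined, foreseeable events that may be serious: "Complications (i.e. AEs and SAEs that are anticipated in the routine treatment pathway, and that we have predefined". Such events "do not need to be reported immediately, provided they are recorded in the 'Complications' section of the Case Report Forms and/or Patient Questionnaires". The waiver covers the timing of reporting; recording is still required.

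The predefined events fall into two lists. The first applies to any child and names no nerve event: "General complications – pain, pressure areas or elbow stiffness, symptomatic instability or nonunion of the bone fragments". The second applies to surgery and is the only place where the ulna nerve appears: "Complications specifically related to surgery - wound infection, injury/irritation to the ulna nerve, implant irritation", followed by further metalwork items.

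Protocol 8.2 sets the expedited route: "only unexpected SAEs potentially related to the intervention will be reported immediately to the Central Trial Team". The principal investigator judges causality first and expectedness second. The chief investigator or a delegate confirms. If disagreement on expectedness persists, one assessor's view that the event is unexpected is enough to class it so.

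In the SAP, Table 11 (section 6.7) assesses expectedness by reference to the intervention. Table 10 (section 6.1) compares complications and SAEs by allocation, with columns for raw and adjusted odds ratios and a p-value. Those cells carry dashes for the number of unforeseeable SAEs but are open for "Participants with unforeseeable SAEs". The complications part of Table 10 has a row that is not limited to surgery, beginning "Ulna nerve problems (little & ring".

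SAP 6.7 also states: "Adverse events that are foreseeable and are not SAEs are recorded in the Complications section and are reported as outcomes".

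**The concern.** A between-arm test is interpretable only if the same event is counted by the same rule in both arms. Here the row selects on foreseeability, and for one event that either arm can have, the documents make foreseeability depend on treatment. The row could then show more unforeseeable SAEs in the non-operative arm when the true rates are equal.

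This row is the one between-arm test in the table that carries a serious-event label. The protocol's background weighs the risks of surgery, nerve damage among them, against possible benefit. A lopsided odds ratio on that row would therefore be easy to misread.

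Separately, the two documents disagree on where a foreseeable SAE is recorded, which affects how any serious-harm row is built.

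**Working it through.** **Step 1. Follow one event through the rules.** Take an ulna nerve problem that leads to readmission, so that it is serious under Protocol 8.1.

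| Step | After surgery | After non-operative treatment |
|---|---|---|
| On an 8.3 list? | Yes, surgical list | No; the general list has no nerve event |
| Expectedness (8.2, Table 11) | Foreseeable | Can be judged unexpected |
| Enters the unforeseeable-SAE row? | No | Yes, if judged potentially related |
| Enters the ulna nerve row of Table 10? | Yes | Yes |

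No passage says how a serious ulna nerve event without surgery is to be classed.

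**Step 2. Count the items that cause the problem.** The general list has 5 items and the surgical list 6, so 11 in all. Five of the surgical items (wound infection, implant irritation, screw cut-out, broken or retained metalwork, metalwork removal) need an operation to occur. Only 1 of the 11, ulna nerve injury or irritation, can arise in both arms and be classed differently.

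**Step 3. Arm size.** SAP 3.3 uses a difference of 4, SD 10, 90% power and 5% two-sided. The normal formula gives n = 2 × (1.960 + 1.2816)² × 10² / 4² = 131.3, so 132 per arm. The t-based calculation gives 132.3, so 133 per arm and 266 in total, as stated. Allowing 20% loss, 133 / 0.8 = 166.25, so 167 per arm and 334 in total, as stated.

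**Step 4. Illustrate the size.** The documents give no rate for serious ulna nerve events. Assume a rate p equal in both arms, from 0.5% to 5%. The expected count from this cause is 167 × p × q in the non-operative arm and 0 in the operative arm, where q is the share of non-operative events judged related and unexpected. Fisher's exact test gives p = 0.061 for 5 v 0 and p = 0.030 for 6 v 0, so six participants are needed. The chance of a spurious significant result from these events alone is P(X ≥ 6), with X binomial(167, p × q).

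| True rate p | Expected, q = 1 | P(X ≥ 6), q = 1 | Expected, q = 0.5 | P(X ≥ 6), q = 0.5 |
|---|---|---|---|---|
| 0.5% | 0.8 v 0 | < 0.1% | – | – |
| 1% | 1.7 v 0 | 0.7% | 0.8 v 0 | < 0.1% |
| 2% | 3.3 v 0 | 12% | 1.7 v 0 | 0.7% |
| 3% | 5.0 v 0 | 39% | 2.5 v 0 | 4% |
| 5% | 8.4 v 0 | 85% | 4.2 v 0 | 24% |

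**Step 5. The odds ratio with other SAEs present.** Let s be the rate of other unforeseeable SAEs, equal in both arms, and take q = 1. Then OR (operative v non-operative) = [s/(1−s)] / [(s+p)/(1−s−p)], with a true value of 1. For s = 0.5% and p = 1%: (0.005/0.995) / (0.015/0.985) = 0.33.

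| s | p = 1% | p = 2% | p = 3% |
|---|---|---|---|
| 0.5% | 0.33 | 0.20 | 0.14 |
| 1% | 0.49 | 0.33 | 0.24 |
| 2% | 0.66 | 0.49 | 0.39 |

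These figures show direction and sensitivity only. Every rate in them is assumed, and q = 1 is the extreme case.

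**Step 6. SAP 6.7 against Protocol 8.3.** Protocol 8.3 sends foreseeable AEs and foreseeable SAEs to Complications. SAP 6.7 sends there only foreseeable events that are not SAEs, and its closing note restricts the SAE listing to unexpected, potentially related events. Read literally, the SAP gives a foreseeable SAE no stated place.

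**The case against.** The strongest reply is that Table 10 already contains arm-neutral comparisons. The ulna nerve row, the nerve-exploration rows and the row for participants with unplanned surgery or admission do not depend on expectedness or relatedness, and their odds ratio cells are open too. A nerve problem needing admission in either arm is counted there. This stands, and it limits the damage to one row.

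The tilt is also conditional. The 8.3 list is introduced as a set of inclusions and need not be exhaustive. A nerve injury put down to the fracture itself is not related to treatment and never enters the row. The surgical list follows surgery received, so a child allocated to non-operative treatment who crosses over falls under it, while Table 10 is laid out by allocation. All of this stands.

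Three stronger readings are tempting, and the documents do not support them:

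- A reader might infer that surgical harms are removed from SAE reporting. Section 8.3 waives immediate reporting only, and such events must still be recorded.
- A reader might take the 6 surgical items out of 11 as the size of the bias. That counts list entries, not events, and five of the six cannot occur without an operation.
- A reader might infer from SAP 6.7 that foreseeable SAEs are lost. SAP 6.1 includes admissions to manage complications among the complications to be noted, and footnote 4 of Table 11 allows an expected category. What remains is a contradiction in wording.

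The row's label and Table 11's column heading do disclose the dependence on the intervention. They do not make the test interpretable.

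**Conclusion.** The point holds in a limited form. The plan would test, by odds ratio and p-value, a row whose inclusion rule for serious ulna nerve events depends on the treatment received. At low event rates the likely result is a small, lopsided count and an unstable odds ratio, not a false significant result: about 1.7 v 0 participants at 1%, with a 0.7% chance of p ≤ 0.05. Larger distortion needs rates of about 2% or more and most non-operative events judged related and unexpected; the documents support neither assumption.

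The primary outcome and estimand are untouched. The events remain visible elsewhere in Table 10, so the report as a whole does not hide them. The contradiction between SAP 6.7 and Protocol 8.3 is plain on the text and does not depend on any assumed rate.

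**What to change.** Change the SAP as follows:

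- Report unforeseeable SAEs descriptively, with the Table 11 listing and counts by arm, and remove the odds ratio and p-value from that row of Table 10.
- Compare serious harm on one row defined identically in both arms. An example is participants with any recorded serious elbow- or treatment-related event, whatever its expectedness, built from SAE forms plus unplanned admissions and reoperations recorded under Complications, excluding the index admission.
- State beside that row that unrelated SAEs are not fully captured, because the SAE forms are for events judged related.
- Reconcile SAP 6.7 with Protocol 8.3 on where foreseeable SAEs are recorded.

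Protocol 8.3 and Table 10 should also be reconciled on how an ulna nerve event without surgery is classed. This review does not say how, and proposes no change to which events need expedited reporting.

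The cost is SAP wording and one derived row from data already collected. The operative arm's serious-event count may look less favourable, and the new row will partly overlap the existing row for unplanned surgery and admissions.

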9.1 Data collection and storage

The Case Report Forms will be designed by the trial manager in conjunction with the trial management team. Patients will be asked to provide their contact details (if applicable) as well as the contact details of up to two alternative friends or family members. Experience from numerous orthopaedic trauma trials has highlighted that collection of this additional data reduces loss to follow-up substantially. The secondary contact will be automatically notified, and they will be given the opportunity to give consent

for us to hold their contact details or request that they are removed. If they have not responded within 14 days, their contact details will be automatically deleted.

Data will be collected in electronic format with direct entry onto the trial database, including the collection of documentary evidence of consent and assent. Electronic data collection has the major advantage of building "data logic" into forms, minimising missing data, data input errors and ensuring the completeness of consent and assent forms. All data entered will be encrypted in transit between the client and server. All electronic patient-identifiable information will be held on a server located in an access-controlled server room at the University of Oxford. The data will be entered into a GCP compliant data collection system and stored in a database on the secure server, accessible only to the research team based on their role within the study. The database and server are backed up to a secure location on a regular basis.

Details of the data collected, where it is stored and who has access to it along with a fair processing statement will be available for the public to see on the study website.

Paper forms, if collected, with patient/parent/guardian-identifiable information will be held in secure, locked filing cabinets within a restricted area at sites. The identifiable data will be kept separately from the outcome data obtained from/about the patients (both paper and electronic). Patients will be identified by a trial ID only. Direct access to source data/documents will be required for trial-related monitoring and/or audit by the Sponsor, NHS Trust/international site or regulatory authorities as required. All paper and electronic data will be retained for at least one year after completion of the trial.

In Australia and New Zealand, contact details will be retained for a minimum of one year after the 12 month follow up period is complete. Completed Consent, Child Consent and/or Assent forms will be kept until the youngest participant reaches 25 years of age (Australia) or 26 years of age (New Zealand).

In the UK, contact details will be retained until the long term follow up is complete (when the child reaches skeletal maturity at 16 years of age). Consent/Assent forms will be kept until the youngest participant reaches 21 years of age.

In the UK, audio recordings of qualitative interviews will be electronically transcribed, and the anonymised transcriptions stored on secure servers at the University of Oxford, identified by a trial ID and/or initials only.

The trial will be reported in line with the CONSORT statement and the appropriate extensions including non-pharmacological and patient reported outcomes.

9.2 Source Data

Source documents are where data are first recorded, and from which participants' CRF data are obtained. These include, but are not limited to, hospital records (from which medical history and previous and concurrent medication may be summarised into the CRF), clinical and office charts, laboratory records, diaries, microfiches, radiographs, audio recordings and patient-reported outcome measures that are submitted directly to the sponsor and correspondence.

CRF entries will be considered source data if the CRF is the site of the original recording (e.g. there is no other written or electronic record of data). All documents will be stored safely in confidential conditions. On all study specific documents, other than the signed consent, the participant will be referred to by their study ID, not by name.

